6.3.2 Hematology

Patients' **WBC, Absolute Lymphocyte Count, Platelet, Absolute Neutrophil Count and Hemoglobin** values will be tabulated by calculating mean and standart deviation and compared as Visit 1 vs. Visit 2 and Visit 1 vs. Visit 3 by using appropriate statistical test. Wilcoxon test will be used in the dependent variables with non-normal distributions whereas Paired sample t test will be used in the dependent variables with normal distributions.

6.4 ASSESSMENTS OF SCALE

Patients' **EDSS, PASAT, SDMT, 9-hole peg test** and **timed 25-foot walk test** values will be tabulated by calculating mean and standart deviation and compared as Visit 1 vs. Visit 3 by using appropriate statistical test. Wilcoxon test will be used in the dependent variables with non-normal distributions whereas Paired sample t test will be used in the dependent variables with normal distributions.

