Exclusion criteria	
Patients fulfilling any of the following criteria are not eligible for inclusion in this study. No additional exclusions may be applied by the investigator, in order to ensure that the study population will be representative of all eligible patients.
 

1. Patients with secondary progressive MS.

2. Patients with known contraindications for fingolimod treatment.

3. Other coexistent autoimmune diseases including Hashimoto thyroiditis, systemic lupus erythematosus, rheumatoid arthritis, psoriasis etc.

4. Patients with any of the following cardiovascular conditions:

• Resting heart rate < 45 bpm/min

• Cardiac failure at any time during the first study visit (Class III as per NYHA classification) or significant heart disease as judged by the physician

• Myocardial infarction during the last 6 months

• History of Mobitz Type II grade 2 AV block

• Past or current grade 3 AV block

• Confirmed history of sick sinus syndrome or sino-atrial heart block

• arrhythmia requiring current treatment with Class Ia drugs (disopyramide, procainamide, quinidine)

• hypertension uncontrolled with medication

5. History of malignancy of any organ system other than localized basal cell carcinoma of the skin.

6. Pregnant or nursing (lactating) women

7. Negative for varicella-zoster virus IgG antibodies at screening

8. History of previous fingolimod therapy

9. Presence of any clinically active infections

Investigational and reference therapy	Fingolimod

Efficacy assessments	EDSS, PASAT, SDMT, 9-hole peg test, timed 25-foot walk and relapse rate
Safety assessments	This study does not include any planned safety analysis
Other assessments	Not Applicable
Data analysis	Data analysis will be performed after all of the data is collected from the enrolled patients. All MS patients and control group will be accepted as the analysis sets. Cytokine and chemokine levels will be analyzed cumulatively at the end of the study. The results will be recorded to the blood sampling logs and laboratory logs cumulatively.
Key words	RRMS, Fingolimod, Cytokine, Chemokine

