### **3.4 Rationale for choice of comparator**

A comparator arm is not applicable for this study

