## **5 Treatment**

### **5.1 Protocol requested treatment**

#### **5.1.1 Investigational treatment**

Treatment will be 0.5 mg p.o fingolimod daily for the treatment arm. The study drug will be provided by Novartis .

Control group will not receive any treatment.

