**Table 6-2 Assessment schedule for Healthy Control Group**

Visit	1	2	3
Day	0	90±7	180±14
Obtain Informed Consent	X		
Evaluation of Inclusion/Exclusion Criteria	X		
Collecting Serum and Blood Samples	X		

Patients should be seen for all visits on the designated day with an allowed “visit window” of “7” days at visit 2 and “14” days at visit 3 , or as close to it as possible, or as shortly after it as possible, or as shortly before it as possible, etc.

At a minimum, patients will be contacted for safety evaluations during the 30 days following the last study visit or following the last administration of study treatment if there are post-treatment follow-up visits (whichever is later), including a final contact at the 30-day point. Documentation of attempts to contact the patient should be recorded in the source documentation.

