### **6.6      Other assessments**

For clinical measures; EDSS and relapses will be recorded after 6 months of treatment. EDSS scoring will also be performed at study entry. PASAT, 9-Hole Peg test, timed 25-foot walk and SDMT tests will be performed only at study entry and termination after 6 months.

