## **14 Appendix 2: Instructions for the Paced Auditory Serial Addition Test (PASAT)**

The PASAT is a measure of cognitive function that specifically assesses auditory information processing speed and flexibility, as well as calculation ability. The PASAT is the last measure administered at each visit. It is presented on audio CD to control the rate of stimulus presentation. Single digits are presented every 3 seconds and the patient must add each new digit to the one immediately prior to it. The test result is the number of correct sums given (out of 60 possible). To minimize familiarity with stimulus items in clinical trials and other serial studies, two alternate forms have been developed; the order of these should be counterbalanced across testing sessions.

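### SAP 6.4 tests Visit 1 to Visit 3 change on PASAT, SDMT and the peg test in treated patients only, so any practice gain would be counted in full and could be read as a fingolimod benefit

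*SAP*

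**What the plan says.** The protocol synopsis lists the efficacy assessments as "EDSS, PASAT, SDMT, 9-hole peg test, timed 25-foot walk and relapse rate". Protocol 6.6 fixes the timing: "PASAT, 9-Hole Peg test, timed 25-foot walk and SDMT tests will be performed only at study entry and termination after 6 months". Table 6-1 agrees, with these tests marked at Visit 1 (day 0) and Visit 3 (day 180) and no practice session shown.

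SAP 6.4 then covers EDSS, PASAT, SDMT, the peg test and the walk in one sentence: the "values will be tabulated by calculating mean and standart deviation and compared as Visit 1 vs. Visit 3 by using appropriate statistical test". The test is a paired t test, or Wilcoxon if the distribution is non-normal. No comparator, adjustment or caveat about repeat testing is given.

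No untreated person is tested twice. Protocol 5.1.1 says the "Control group will not receive any treatment", and Table 6-2 ("Assessment schedule for Healthy Control Group") gives controls only consent, an eligibility check and one blood collection at day 0. Protocol 3.4 adds: "A comparator arm is not applicable for this study".

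Repeat testing is recognised in one place. For PASAT, Appendix 2 says: "To minimize familiarity with stimulus items in clinical trials and other serial studies, two alternate forms have been developed", with their order to be counterbalanced. The documents contain nothing similar for SDMT or the peg test.

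The synopsis and Protocol 3.2 both state that the design, though neither randomized nor blinded, is free of bias because each patient acts as his or her own control.

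**The concern.** Pairing removes stable differences between patients. It does not remove anything that moves all patients' second scores in the same direction. A practice effect does that, and by definition it moves scores towards better performance. In a single treated group it cannot be told apart from a drug effect.

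The alternate PASAT forms deal with memory for the items. Appendix 2 does not say that they deal with learning how to do the task.

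Practice is one of several such components. Regression to the mean and natural course enter the same contrast, for EDSS and the walk as well. Two of the three eligibility routes in Protocol 4.1 select patients on recent attacks, MRI activity or treatment failure, so a shift from selection is possible.

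At stake is how SAP 6.4 is read. A significant change on a listed efficacy assessment could be reported as a benefit of fingolimod when the design cannot support that.

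**Working it through.** **The plan's own figure.** The only powered figure is 50 pairs for IL-17 (Protocol 9.8, SAP 5.1): difference 7 pg/ml, SD 15 pg/ml, alpha 0.05, power 90%. Treating 15 as the SD of the paired differences, with a two-sided test:

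n = ((1.960 + 1.282) × 15 / 7)² = 48.2, so 49 pairs. The exact paired t calculation gives 51, and power at 50 pairs is 89.9%.

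The figure reproduces to within 2 pairs. It does not concern the scales, and it is used here only to confirm the paired-test method.

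**What the tested change contains.** For a scale score Y:

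E(Y at Visit 3 − Y at Visit 1) = drug effect + practice + regression to the mean + natural course.

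SAP 6.4 tests this sum against zero. With no untreated retest group, the terms cannot be separated.

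**Inputs for the size of a practice shift**

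- Pairs: 60 patients (Protocol 9.8), or 60 × (1 − 0.20) = 48 after the plan's 20% dropout. Protocol 5.4.9 says withdrawn patients are replaced, so 60 completers is possible.
- Alpha: 0.05 two-sided. This is assumed, because SAP 6.4 states no level for the scales.
- Practice gain g: 0.1, 0.2 or 0.3 baseline SD. Assumed.
- Test-retest correlation r: 0.8, range 0.7 to 0.9. Assumed.
- Drug effect, regression to the mean and natural course: all set to zero.

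**Formula.** With equal SDs at the two visits, the SD of change is √(2(1 − r)) baseline SDs. The standardised shift is δ = g / √(2(1 − r)). The chance of a significant improvement is P(T > t₀.₉₇₅,ₙ₋₁), where T is noncentral t with n − 1 degrees of freedom and noncentrality δ√n.

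**Worked case, n = 60, r = 0.8.** SD of change = √0.4 = 0.632. For the three gains, δ = 0.158, 0.316 and 0.474, and δ√60 = 1.22, 2.45 and 3.67. The critical value is 2.001. The probabilities are 0.225, 0.673 and 0.951. With no shift of any kind, the probability in this direction is 0.025.

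| Pairs | r | g = 0.1 | g = 0.2 | g = 0.3 |
|---|---|---|---|---|
| 60 | 0.7 | 16% | 50% | 84% |
| 60 | 0.8 | 23% | 67% | 95% |
| 60 | 0.9 | 40% | 93% | 99.9% |
| 48 | 0.7 | 14% | 42% | 75% |
| 48 | 0.8 | 19% | 57% | 90% |
| 48 | 0.9 | 33% | 86% | 99.5% |

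These are paired t figures. A shift common to all patients also moves the Wilcoxon test, but that was not computed.

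**Observed change needed for significance.** At n = 60 it is 2.001 / √60 = 0.258 SD of change, which at r = 0.8 is 0.258 × 0.632 = 0.16 baseline SD. At n = 48 it is 0.290 SD of change, or 0.18 baseline SD.

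**Effect on the secondary objective.** If every patient gains the same amount c, then corr(X, Y + c) = corr(X, Y), where X is the cytokine change. An equal gain neither biases the association nor adds noise to it. Only a gain that differs between patients adds noise, and the documents give no basis for sizing that.

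**The case against.** The case against giving this much weight is substantial.

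- **No gain is shown.** The tests are about 180 days apart, and nothing in the documents says that scores improve on repetition over that interval. This stands. The point is conditional: if there is a gain, it is counted in full.
- **The sizes are assumptions.** Neither the gain nor the correlation has a source in the documents, and the table runs from 14% to 99.9%. PASAT has alternate forms and a maximum of 60 correct, so one gain need not fit all three tests. This also stands. The table shows sensitivity to a shift and is not a forecast.
- **The role of the tests is limited.** SAP 6.4 tabulates and compares without attributing the change to the drug, and Protocol 9.5 plans no special hypothesis. Protocol 6.4.1 names relapses and EDSS as the key efficacy criteria. Protocol 9.4 does list the scales under its primary-variables heading, but their change over time is neither the primary nor the secondary objective. This limits the weight of the point. It does not remove the risk of misreading, because the synopsis calls these tests efficacy assessments and the protocol says that there is no bias.
- **Practice is only one part of the problem.** This is correct, and the remedy therefore has to cover every uncontrolled component and all five scales.

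A reader might also infer that Visit 1 is each patient's first exposure to these tests. The documents do not say so. Some eligible patients have had at least a year of earlier treatment, and previous testing is neither recorded nor excluded.

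**Conclusion.** The point holds as a statement about confounding. SAP 6.4 tests a change that would include any practice gain in full, together with regression to the mean and natural course. The claim in the synopsis and Protocol 3.2 that self-control leaves no bias does not hold for this contrast.

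The size depends on assumed values. At correlation 0.8, gains of 0.1, 0.2 and 0.3 baseline SD give a significant improvement with no drug effect in about 23%, 67% and 95% of trials with 60 pairs, and in 19%, 57% and 90% with 48 pairs.

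Two stronger readings are not supported. One is that a practice gain will occur and will be reported as a drug benefit; the documents establish neither. The other is that the cytokine prediction analysis is compromised; a gain equal in all patients leaves those correlations unchanged, and the SAP specifies no predictive model that could be examined for harm.

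The primary objective, a comparison of cytokines between patients and controls, is untouched. The correction is worth making because its main part is cheap and governs what may be concluded from listed efficacy assessments.

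**What to change.** **(a) Reporting, possible at any stage.** In SAP 6.4, report the mean Visit 1 to Visit 3 change with a 95% confidence interval for all five scales. State that this change includes any practice gain, regression to the mean and natural course, and that it is not an estimate of fingolimod efficacy. Remove the no-bias statement from the synopsis and Protocol 3.2.

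**(b) Procedure, only if baseline testing is not complete.** By amendment, add one short unscored practice run of PASAT, SDMT and the peg test before the scored Visit 1 test. Use counterbalanced alternate forms for SDMT where they are available, as Appendix 2 already does for PASAT. Alternate forms are a partial guard, since they act on learning of items and not of the task.

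SAP 6.5.1 and 6.5.2 speak of non-normal distributions as already observed, so data may have been in hand when the SAP was written. If baseline testing is finished, only (a) remains.

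**Cost.** The SAP part of (a) is a few sentences and one interval per scale. Removing the no-bias statement and making the changes in (b) need a protocol amendment under Protocol 11.1. Part (b) also adds a few minutes at Visit 1.

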6.5 ASSESSMENT OF CYTOKINE AND CHEMOKINE LEVELS

6.5.1 ELISA

Subjects' **IL-4, IL-6, IL-8, IL-9, IL-10, IL-13, IL-17, IL-23, IFN- γ , TNF- α , VLA4, CCL2, CCL5, CXCR3 and CXCL13** values will be tabulated by calculating mean and standart error and compared as Control group vs. Visit 1 (MS patients), Visit 1 (MS patients) vs. Visit 2 (MS patients), Visit 1 (MS patients) vs. Visit 3 (MS patients) and Control group vs. Visit 3 (MS patients) by using appropriate statistical test. Mann Whitney U test with significance level of 0.05 was used for the independent variables since non-normal distributions had been observed. Wilcoxon test was used for the dependent variables with non-normal distributions. For the independent variables with normal distributions Independent Sample t test was used whereas Paired sample t test was used for the dependent variables with normal distributions.

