## **9.5 Statistical model, hypothesis, and method of analysis**

There is no special hypothesis planned for this study.

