3 OBJECTIVES OF THE STUDY

3.1. PRIMARY OBJECTIVE

The primary objective of this study is to evaluate the differences between serum cytokine and chemokine levels of healthy controls and multiple sclerosis patients.

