6.1 DEMOGRAPHICS

- **Gender:** Subjects, male and female, in both groups (Control & MS patients) will be expressed separately as n and %.
- **Age:** Age data for subjects in the “Control” and in the “MS patients” groups will be tabulated by calculating n, mean, standard deviation, minimum, maximum and median.

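### All biomarkers are summarised by mean and standard error only, even where rank tests are used, and no effect estimate or confidence interval is planned for any of the four contrasts

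*SAP*

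**What the plan says.** The primary objective in SAP 3.1 is to "evaluate the differences between serum cytokine and chemokine levels of healthy controls and multiple sclerosis patients"; Protocol 2.1 says the same.

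SAP 6.5.1 covers 15 serum markers and SAP 6.5.2 covers 8 intracellular markers. Both sections state that values will be "tabulated by calculating mean and standart error". Both list the same four contrasts: control vs Visit 1, Visit 1 vs Visit 2, Visit 1 vs Visit 3, and control vs Visit 3. Each contrast receives a test and nothing more.

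On the choice of test, SAP 6.5.1 says: "Mann Whitney U test with significance level of 0.05 was used for the independent variables since non-normal distributions had been observed". Wilcoxon is named for non-normal paired data. The t tests are kept for the rest: "For the independent variables with normal distributions Independent Sample t test was used", with a paired t test for dependent data. No individual marker is assigned to either class.

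The protocol does not fill the gap. Section 9.4 lists the variables to be analysed, 9.5 states "There is no special hypothesis planned for this study", and 9.6 marks supportive analyses as not applicable.

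Elsewhere the SAP uses the SD. Age in 6.1 is "tabulated by calculating n, mean, standard deviation, minimum, maximum and median", and 6.2 treats the numerical MS-history variables in the same way. The scales in 6.4 are "tabulated by calculating mean and standart deviation", as are chemistry and haematology in 6.3.

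**The concern.** Three things do not fit together.

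- **Summary and test.** A rank test does not compare means. Where a marker is skewed, a few high values pull the mean, so the tabulated means need not show the difference that the p-value refers to. In principle the two can point in opposite directions.
- **SE in one section, SD in the others.** The SE describes how precisely a mean is estimated. The SD, quartiles and range describe how patients vary. The biomarkers, which carry the primary objective, are the only variables given an SE. A reader coming from the SD tables can easily take it for spread. SAP 6.5 does not list n among the statistics to be shown, so converting SE to SD is not assured either.
- **No estimate.** The objective is to evaluate differences, and no special hypothesis is planned, so the study is largely descriptive. A descriptive study needs the size and precision of each difference. A p-value alone does not separate a marker with little difference from one that was measured too imprecisely to tell.

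The paired contrasts suffer most. Protocol 1.2 gives the on-treatment shift in cytokines as a main purpose, and the precision of a within-patient change cannot be worked out from two visit-level SEs.

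**Working it through.** **Inputs.** From SAP 5.1 and Protocol 9.8: IL-17 mean 32 pg/ml and SD 15 pg/ml in RRMS patients (described there as normal), difference 7 pg/ml for matched pairs, power 90%, alpha 0.05, 50 pairs, at least 60 enrolled per group. SAP 4 gives 80 patients and 60 controls. My assumptions: two-sided alpha, and the same SD of 15 in controls, for whom the documents give none.

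**The plan's own figure.** With 15 used as the SD of the paired difference:

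n = ((1.960 + 1.282) × 15 / 7)² = 48.2, rounded up to 49. By the noncentral t, power at 50 pairs is 89.9%. The stated 50 is reproduced, so the inputs are read as intended.

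**What the table would show.** SE = SD/√n.

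- n = 50: 15/√50 = 2.12
- n = 60: 15/√60 = 1.94
- n = 80: 15/√80 = 1.68

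At n = 60 the entry would be 32 with an SE of 1.9, and the SD is √60 = 7.7 times larger.

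**Precision of the group difference.** SE of the difference = 15 × √(1/n₁ + 1/n₂); half-width = t × SE.

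| Patients / controls | SE of difference | t (0.975) | 95% half-width |
|---|---|---|---|
| 80 / 60 | 2.56 | 1.98 | 5.1 |
| 60 / 60 | 2.74 | 1.98 | 5.4 |
| 50 / 50 | 3.00 | 1.98 | 6.0 |

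A simulated Hodges-Lehmann interval (normal data, 60/60) has a half-width of about 5.5, so matching the estimate to the rank test costs little precision.

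As a yardstick, take the planning difference of 7. At 60/60, an observed difference of 3 pg/ml would have an interval of 3 − 5.4 = −2.4 to 3 + 5.4 = 8.4. That is non-significant, yet it still includes 7. The planned output would not show this directly.

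**Which contrasts can be recovered from the planned table.** Patients and controls are independent groups, so the two SEs combine: √(1.94² + 1.94²) = 2.74, and 1.98 × 2.74 = 5.4. This works for control vs Visit 1 and, in the same way, control vs Visit 3.

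For Visit 1 vs Visit 2 or Visit 3, the SE of the change is √(SE₁² + SE₂² − 2r·SE₁·SE₂). It depends on the within-patient correlation r, which the table does not give. With both SEs at 1.94 (1.94² = 3.75) it is √(7.5 × (1 − r)):

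- r = 0: 2.74
- r = 0.5: 1.94
- r = 0.8: 1.22

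The same table entries fit any of these.

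**How far a mean can lie from the typical value.** This is an assumption, not a figure from the plan. For a lognormal marker with mean 32, the median is 32/√(1 + CV²):

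- CV 0.47 (the plan's 15/32): 29.0
- CV 1: 22.6
- CV 2: 14.3

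With mild skew the mean is adequate. With strong skew it is more than twice the median.

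**The case against.** A fair defence runs as follows.

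- Group means are tabulated, so the plan offers more than p-values. A labelled SE is a legitimate measure of precision, and for patients vs controls a reader can subtract the means and combine the SEs. This stands, and it narrows the point. What remains is that the derived figure is unplanned, is on the mean scale, and does not match a rank test.
- The t tests are kept for normally distributed markers, and for those the mean is the right summary. This stands. The mismatch concerns the non-normal subset, which the SAP does not name. The missing estimate and interval concern every marker.
- The numerical example uses IL-17, the one marker the documents call normal, and borrows the patient SD for controls. This stands. The figures illustrate scale and do not measure any skewed marker.
- Chemistry, haematology and the clinical scales (SAP 6.3 and 6.4) also have tests without effect estimates. This stands too. Only the choice of SE over SD is particular to 6.5. The gap matters more there because those variables carry the primary objective.

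A reader might infer more: that the primary objective will yield nothing but p-values and misleadingly small error bars, or that the interval for patients vs controls could never be known. The documents do not support this. Means are planned, the crude interval can be derived, and no biomarker graph is specified, so there are no error bars to criticise. Nor do they support the reading that every biomarker is non-normal.

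**Conclusion.** The point holds as a minor reporting weakness. SAP 6.5.1 and 6.5.2 give mean and SE only for all 23 markers, whatever the test, and plan no estimate or interval for any of the four contrasts. Three consequences follow:

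- For non-normal markers, the summary does not match the rank test.
- The SE invites misreading beside SD-based tables.
- The precision of the two paired changes is lost. For the two contrasts with controls, only a crude, unplanned mean difference could be derived.

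The sizes above rest on an SD of 15 pg/ml in both groups and on a marker described as normal, so they are illustrative. The planning difference of 7 was set for matched pairs and serves here only as a yardstick. That a mean and a rank test may point in opposite directions is a general possibility; nothing in the documents shows that it happens here. The tests, the sample size and the type I error are unaffected.

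**What to change.** In SAP 6.5.1 and 6.5.2:

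1. Tabulate n, median and quartiles for every marker and time point. Give the SD in place of the SE or beside it. Keep the mean for markers analysed by t test: the medians are an addition and do not replace it.
2. For each of the four contrasts, report an estimate with a 95% CI that matches the test used: the Hodges-Lehmann shift with Mann-Whitney or Wilcoxon, and the mean difference with the independent or paired t test. Compute the paired estimates from within-patient changes.
3. State whether the data had been examined when section 6.5 was written. Its description of the tests and of the observed non-normality is in the past tense, which suggests that they had. If so, label the added estimates as post hoc.

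The cost is SAP wording and table shells, for 23 × 4 = 92 estimates computed from data already being collected. No extra patients, visits or assays are needed.

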## **1.2 Purpose**

The main purpose of this study is to measure the serum levels of major Th1, Th2, Th17 and Treg cytokines as well as cytokines and chemokines that are known to be upregulated during multiple sclerosis relapses. Measurements will be performed at 3 time points; i.e. before treatment, 12±1 weeks and 24±2 weeks after fingolimod treatment. By this way, we will be able to test whether fingolimod treatment shifts the cytokine balance from Th1/Th17 to Th2/Treg and reduces the levels of inflammation related cytokines and chemokines. The basal levels of the cytokines will be compared with the cytokine levels of healthy controls.

The second purpose of the study is to test the predictive value of cytokine/chemokine changes measured in the 3rd and 6th months on the EDSS, PASAT, SDMT, 9-hole peg test, timed 25-foot walk test and relapse rate observed after 6 months of treatment.

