## **9.4 Analysis of the primary variable(s)**

Serum IL-4, IL-6, IL-8, IL-9, IL-10, IL-13, IL-17, IL-23, IFN- $\gamma$ , TNF- $\alpha$ , VLA4, CCL2, CCL5, CXCR3, CXCL13 levels, PBMC intracellular IL-4, IL-6, IL-9, IL-10, IL-13, IL-17, IFN- $\gamma$ , TNF- $\alpha$  levels, EDSS, PASAT, 9-Hole peg test, timed 25-foot walk, SDMT scores and relapse rates will be analyzed.

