## **9.8 Sample size calculation**

Due to the lack of previous studies using all of the cytokines and chemokines and multitudinous analyses, it is difficult to estimate a precise sample size for our study. Despite this, our previous publications indicate that the basal IL-17 concentration is normally distributed with a mean of 32 pg/ml ( $\pm$ stdev of 15 pg/ml) in RRMS patients. If the true difference in the mean concentration of matched pairs is 7 pg/ml, we will need to study 50 pairs of subjects to be able to reject the null hypothesis with a power of 90%. The Type I error probability associated with this test of this null hypothesis is 0,05.

With assumption of drop out rate of 20% minimum 60 RRMS patients and 60 healthy control subjects should enroll to the study. Due to expected high rate of screen failure patients, we decided to screen 80 RRMS patients in order to reach 60 eligible RRMS subjects for the study.

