5 ANALYZED POPULATIONS

The study will include only 80 relapsing remitting MS patients and 60 healthy controls without any known autoimmune disease. RRMS patients will be followed for 6 months.

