6.5.2 Flow Cytometry

Subjects' **IL-4, IL-6, IL-9, IL-10, IL-13, IL-17, IFN- γ and TNF- α** values will be tabulated by calculating mean and standart error and compared as Control group vs. Visit 1 (MS patients), Visit 1 (MS patients) vs. Visit 2 (MS patients), Visit 1 (MS patients) vs. Visit 3 (MS patients) and Control group vs. Visit 3 (MS patients) by using appropriate statistical test. Mann Whitney U test with significance level of 0.05 was used for the independent variables since non-normal distributions had been observed. Wilcoxon test was used for the dependent variables with non-normal distributions. For the independent variables with normal distributions Independent Sample t test was used whereas Paired sample t test was used for the dependent variables with normal distributions.

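### SAP 6.5 plans 92 cytokine comparisons with 0.05 as the only stated level, no visible multiplicity rule or exploratory label, and no settled primary contrast

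*SAP*

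**What the plan says.** SAP 6.5.1 lists 15 serum analytes measured by ELISA, and SAP 6.5.2 lists 8 intracellular analytes measured by flow cytometry. Both use the same four contrasts: "compared as Control group vs. Visit 1 (MS patients), Visit 1 (MS patients) vs. Visit 2 (MS patients"), then Visit 1 vs Visit 3 and Control vs Visit 3. The level is given once in each section, for one test: "Mann Whitney U test with significance level of 0.05 was used for the independent variables since non-normal distributions had been observed". The Wilcoxon and t tests carry no stated level.

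On what is primary, the documents say different things:

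- SAP 3.1 (and Protocol 2.1) aims to "evaluate the differences between serum cytokine and chemokine levels of healthy controls and multiple sclerosis patients". It names no analyte and no visit.
- Protocol 1.2 first describes testing whether the cytokine balance moves under fingolimod, and then adds: "The basal levels of the cytokines will be compared with the cytokine levels of healthy controls". The study title also stresses the effect of the drug.
- Protocol 9.4, headed as the analysis of the primary variables, lists all 15 serum and 8 intracellular markers and continues: "EDSS, PASAT, 9-Hole peg test, timed 25-foot walk, SDMT scores and relapse rates will be analyzed".
- Protocol 9.5 states: "There is no special hypothesis planned for this study". Yet Protocol 9.8 sizes the study to reject a null hypothesis, and says: "The Type I error probability associated with this test of this null hypothesis is 0,05". SAP 5.1 repeats this.

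The sample size sections mention the large number of analyses, but only as a reason why a precise sample size is hard to give. One heading in Protocol section 2 is redacted in the table of contents, so the statement that there is no multiplicity rule applies to the readable text.

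**The concern.** A plan that runs many tests at 0.05 without saying how the set will be read lets any single p-value below 0.05 be reported as a finding. Here the primary objective covers a whole panel, so one chance hit among 15 analytes could be presented as a difference between patients and controls. Because the primary contrast is not settled either, a hit at Control vs Visit 1, at Control vs Visit 3 or in a within-patient change could each be offered as the answer to the main question. What is at stake is the credibility of positive results, most of all if few analytes truly differ.

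**Working it through.** **1. The plan's own figure.** The documents give no error rate for the panel. The one related figure is 50 pairs for IL-17 (Protocol 9.8, SAP 5.1): difference 7 pg/ml, SD 15 pg/ml, type I error 0.05, power 90%. Taking 15 as the SD of the paired differences and a two-sided test, n = (15 × (1.960 + 1.282) / 7)² = 48.2, so 49 pairs. By the exact t calculation, power at 50 pairs is 89.9%. The stated 50 therefore reproduces, and it spends the whole 0.05 on one analyte in one test.

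**2. Number of tests.** 15 × 4 = 60 serum tests and 8 × 4 = 32 flow cytometry tests, 92 together.

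**3. False positives among the 15 serum Control vs Visit 1 tests if no analyte differs.**

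- Expected number: 15 × 0.05 = 0.75, whatever the correlation.
- Chance of at least one, independent tests: 1 − 0.95¹⁵ = 0.537.
- The documents give no correlation between analytes. With equally correlated normal statistics (two-sided, numerical integration) the chance is:

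| Assumed correlation | Chance of at least one p < 0.05 |
|---|---|
| 0 | 54% |
| 0.3 | 46% |
| 0.5 | 36% |
| 0.7 | 26% |
| 0.9 | 14% |

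A simulation of 15 Mann-Whitney tests at 60 vs 60 (4,000 runs per correlation) gave 52.1%, 37.6% and 14.7% at correlations 0, 0.5 and 0.9, in line with the table.

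If all 23 markers in Protocol 9.4 count as primary at this contrast, 23 × 0.05 = 1.15 false positives are expected. The chance of at least one is 1 − 0.95²³ = 69% under independence, 45% at 0.5 and 16% at 0.9.

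**4. When some analytes truly differ.** Assumptions: independent tests, every true difference 7 pg/ml, SD 15 in both groups, 60 per group. This applies the IL-17 figures to every analyte. Results are for 15 tests, by simulation; BH is Benjamini-Hochberg at 5%. The share of false findings is the expected share of false positives among all significant results.

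| Analytes that differ | Any false positive, unadjusted | Any false positive, BH | Share of false findings, unadjusted | Share of false findings, BH |
|---|---|---|---|---|
| 0 | 54% | 5% | 54% | 5.0% |
| 1 | 51% | 7% | 35% | 4.7% |
| 5 | 40% | 12% | 11% | 3.4% |
| 10 | 23% | 11% | 3% | 1.7% |

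At assumed correlations of 0.3 to 0.9 the BH false discovery rate stayed at or below 4.8% in every scenario.

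**5. Price in power.** SAP 5 states "The study will include only 80 relapsing remitting MS patients and 60 healthy controls", while SAP 5.1 speaks of 60 eligible patients out of 80 screened, so both sizes are shown. Power per analyte for 7 pg/ml, all on a t-test basis with SD 15 assumed in both groups:

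| Patients vs controls | Unadjusted | BH, 1 differs | BH, 5 differ | BH, 10 differ |
|---|---|---|---|---|
| 60 vs 60 | 72% | 34% | 47% | 58% |
| 80 vs 60 | 77% | 41% | 56% | 67% |

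**The case against.** The strongest reply is that the study is descriptive. Protocol 9.5 plans no special hypothesis, and the 0.05 stands beside the Mann-Whitney test only, so the 23 × 2 = 46 within-patient tests have no stated level in SAP 6.5. This does not settle the matter. The absence of a special hypothesis is not an exploratory label, the SAP still specifies significance tests, and the sample size sections speak of rejecting a null hypothesis at 0.05. If description is meant, a short wording change would say so.

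The second reply is that a panel with no true differences is unlikely. Some markers were chosen because they rise during relapses, although patients must be at least 2 months past their last relapse. This stands in part: 54% is the upper end, and the share of false findings is small if most analytes differ.

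The third reply is that adjustment is costly, and step 5 of the working bears that out.

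A reader might also infer more than the documents support:

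- *That 54% describes all 92 tests, or that the independence formula can be carried over to 92.* The contrasts share samples: each Visit 1 sample enters three contrasts and each control sample two. The figure is for 15 tests only.
- *That the baseline serum tests are the only primary family and everything else is exploratory.* The stated objective does name controls vs patients, but the title, Protocol 1.2 and the sizing in matched pairs point to the treatment contrasts. The conflict is for the sponsor to settle.
- *That the past tense in SAP 6.5 shows that study data had been seen.* It raises the question; the readable text does not answer it.

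**Conclusion.** The concern holds in this limited form. The readable plan gives no rule for interpreting 92 comparisons, and the documents do not agree on the primary contrast. For the 15 serum Control vs Visit 1 tests with no true difference, 0.75 false positives are expected. The chance of at least one runs from 54% (independence) to 14% (assumed correlation 0.9), above the nominal 5% throughout that range. The benefit of adjustment is large if none or few analytes differ and small if most do. The first result rests on two-sided tests at 0.05 and an assumed common correlation; the second on independence and on one effect size and SD for all analytes. This should be corrected. It does not show that any particular result would be false.

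**What to change.** **In SAP 6.5**, report Benjamini-Hochberg adjusted p-values (5% false discovery rate, two-sided) beside the raw p-values. Do this within each contrast, separately for the 15 serum and the 8 flow cytometry analytes, and base any claim of a difference on the adjusted values. State that this controls the false discovery rate within each family, not the chance of any false positive and not error across all 92 tests.

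**On the primary contrast**, the sponsor should state which one answers the primary objective and reconcile Protocol 1.2, 9.4 and 9.5 with it. The 15 serum Control vs Visit 1 tests fit the stated objective when it is read with Protocol 1.2, but the treatment contrasts should not be demoted by default.

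**On timing**, because SAP 6.5 reports the distributions in the past tense, date the change and state whether data had been seen.

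**Alternative:** if only description is intended, label all 92 p-values exploratory and drop the 0.05 level.

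**Cost:** SAP wording, one adjustment call per family, and a written amendment under Protocol 11.1 for the protocol sections. No new data are needed. The statistical price is the power loss shown in the working; raw p-values remain reported. The descriptive alternative needs wording only.
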